Title page:

Title: Comparison of Clinical and Radiographic Success Between:
Mineral Trioxide Aggregate (MTA) & Ferric Sulfate (FS) Pulpotomies for Primary
Molars.

NCT 02783911

Date: Sep 02, 2014

Statement of Problem

Premature loss of a tooth from caries or trauma can lead to malocclusion and/or to esthetic, phonetic, function problems, super eruption of the opposing tooth and costly procedures to correct and maintain space. A pulpotomy is one type of treatment for vital pulp therapy. The aim of the treatment is to preserve the radicular pulp, avoiding pain and swelling, to retain the tooth and preserve arch integrity.

Formocresol (FC) has a long history for pulpal medicament with a success rate of up to 97%. Its use, however, has been questioned due to published studies raising concerns for systemic distribution, carcinogenicity, mutagenicity, and immune sensitization. These concerns have led to the search and use of different materials and techniques to replace FC as a pulpal medicament that is cost effective, safe, and predictable. Calcium hydroxide, diluted formocresol, electrosurgery, lasers, ferric sulfate (FS), mineral trioxide aggregate (MTA), and sodium hypochlorite have been used as alternatives to FC for pulp therapy. Of these alternatives, MTA and FS have the most similar clinical and radiographic success as FC but the number of studies evaluating their success is limited in primary teeth. There has not been any study comparing MTA to FS for use in primary molar pulpotomies.

The purpose of this study is to evaluate which of these materials, gray MTA (GMTA) or FS, has the best long-term success rates with the least amount of adverse effects in primary molar pulpotomies. We will clinically and radiographically compare the success rates of MTA and ferric sulfate pulpotomies in primary teeth.

Review of Literature

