Follow-up appointments at 6 months, 9 months, and 12 months will be completed for subjects. The follow-up appointments will consist of a clinical examination and bite-wing view periapical radiographs to determine success(s)/failure(s) of two different pulpotomized teeth.

The criteria for a successful pulpotomy will include:

- retained for the length of the study or exfoliate naturally
- normal bone trabeculation in the periapical region
- no abscess or fistula
- contained internal resorption is acceptable
- calcific metamorphosis is acceptable

When the teeth exfoliate or require extraction, the teeth with pulpotomies will be collected and histologic slices will be completed to analyze for what types if any cellular changes from the use of the pulpal medicaments.

Statistical Analysis:

Data and statistical analysis will include descriptive and inferential statistics. Inferential statistical analysis will use SPSS 16 (SPSS, Chicago, IL) with a significance level set at $P \leq 0.05$

Budget:

Item	Units Needed	Price/Unit	Total Price
Patient incentive – follow-up visits	60	\$50	\$3000
Mineral Trioxide Aggregate	5 dose packets	\$475	\$475
Ferric Sulfate	1	\$35	\$35
3M Stainless steel crowns	60	\$5	\$300
Copying, stationery , paper, pen, 2 clip board			\$300.00
Total			\$4,110

Proposed Research Milestones:

Continuation of Established IRB#: 5140262

March 2016:

- Data collection

March 2016:

- Proposal preparation and submission for approval by the Research Guidance Committee

April 2016:

- Protocol preparation, submission, and approval by Loma Linda University School of Dentistry Research Committee

June 2016- June 2017:

- Data analysis and article preparation for review and submission

References:

- Casamassimo, P. S. (2013). Pediatric Dentistry Infancy Through Adolescence. St. Louis, Missouri, Elsevier Saunders.
- Chen, J. W. (2012). "Materials for primary tooth pulp treatment: the present and the future." Endodontic Topics 2012 **23**: 41-49.

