Title page:

Title: Comparison of Clinical and Radiographic Success Between:
Mineral Trioxide Aggregate (MTA) & Ferric Sulfate (FS) Pulpotomies for Primary Molars.

NCT 02783911

Date: Sep 02, 2014

Comparison of Mineral Trioxide Aggregate and Ferric Sulfate:
Pulpal Medicaments for Pulpotomized Primary Teeth

Statistical analysis plan

The following clinical information were collected from the charts: Mobility, pain, abscess/draining fistula, and facial swelling. Exfoliation of the pulp treated teeth was recorded and graded as normal, early, or delayed based on the age of the patient at the time of the recall and on the exfoliation status of the contralateral tooth. If there is any clinical signs of the above the tooth will be count as clinical failure.

Data was analyzed using the Statistical Package for Social Sciences v 16.0 (SPSS Inc., Chicago, Ill). The difference between the materials was analyzed using chi-square, Significance level was set $P < .05$.

Chi-Square Tests

	Value	df	Asymptotic Significance (2- sided)	Exact Sig. (2- sided)	Exact Sig. (1- sided)
Pearson Chi-Square	.059 ^a	1	.808		
Continuity Correction ^b	.000	1	1.000		
Likelihood Ratio	.060	1	.807		
Fisher's Exact Test				1.000	.603
Linear-by-Linear Association	.057	1	.812		
N of Valid Cases	24				

a. 2 cells (50.0%) have expected count less than 5. The minimum expected count is 2.25.

b. Computed only for a 2x2 table

Summary: The result showed there is no statistical difference in long term clinical success between the two pulpotomy medicaments. (MTA vs FS)

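### The SAP's only conclusion is a non-significant test in 24 cases, with no success rate per arm, difference or confidence interval; gaps above 30 points either way remain open

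*SAP*

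**What the plan says.** The purpose, in the protocol's Statement of Problem, is "to evaluate which of these materials, gray MTA (GMTA) or FS, has the best long-term success rates". On method, the protocol's Statistical Analysis section says only "Data and statistical analysis will include descriptive and inferential statistics", plus the software and a 0.05 significance level. It names no effect measure and no interval. On timing, Methods and Materials says "Follow-up appointments at 6 months, 9 months, and 12 months will be completed for subjects".

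The SAP names the test: "The difference between the materials was analyzed using chi-square". It prints the Chi-Square Tests table for 24 valid cases: Pearson .059 (p = .808), continuity-corrected .000 (p = 1.000), likelihood ratio .060 (p = .807), Fisher 1.000 two-sided and .603 one-sided, and linear-by-linear .057 (p = .812). A footnote adds "2 cells (50.0%) have expected count less than 5. The minimum expected count is 2.25". The Summary then reads "The result showed there is no statistical difference in long term clinical success between the two pulpotomy medicaments".

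The SAP contains no crosstabulation, arm sizes, success rates, difference or interval. Neither document sets an equivalence or non-inferiority margin. The SAP's only reference to assessment time is in its grading of exfoliation, "based on the age of the patient at the time of the recall", and it does not say when that recall took place.

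**The concern.** A question about which success rate is higher calls for two rates and a statement of how precisely their difference is known. A p-value of .808 supplies neither: it can come from a precise estimate near zero or from too few cases to tell. With 24 cases and failures or successes in single figures, the second is the obvious worry. A reader who takes the Summary as evidence that the two materials perform alike would be drawing a conclusion that the data may not support.

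The reader cannot correct this alone, because the output does not show which margin is treatment, which arm is MTA or which column is success. The words about long-term success have a similar gap: planned visits stop at 12 months, and the time at which these 24 cases were assessed is not given.

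**Working it through.** **1. Recover the table from the printed output.** Inputs from the SAP: N = 24, minimum expected count 2.25, two expected counts below 5, Pearson .059.

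The minimum expected count is (smaller row total x smaller column total)/N, so the product of the two smaller totals is 2.25 x 24 = 54. Neither can exceed 12. The factor pairs of 54 are 1 x 54, 2 x 27, 3 x 18 and 6 x 9, and only 6 and 9 qualify. The margins are therefore 6/18 and 9/15.

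The expected counts are 2.25, 3.75, 6.75 and 11.25, two of them below 5 as the footnote says. With a as the count in the smallest-expectation cell:

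Pearson = (a - 2.25)² x (1/2.25 + 1/3.75 + 1/6.75 + 1/11.25) = (a - 2.25)² x 0.948

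- a = 1 gives 1.481
- a = 2 gives 0.0593
- a = 3 gives 0.533

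Only a = 2 matches, so the cells are 2, 4, 7 and 11. A full enumeration of 2x2 tables with N = 24 agrees: eight tables fit, all relabellings of these four counts.

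**2. Reproduce the SAP's own figures.**

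| Statistic | SAP | Recomputed |
|---|---|---|
| Pearson | .059, p .808 | 0.0593, p 0.8077 |
| Continuity-corrected | .000, p 1.000 | 0.000, p 1.000 |
| Likelihood ratio | .060, p .807 | 0.0599, p 0.8066 |
| Linear-by-linear (Pearson x 23/24) | .057, p .812 | 0.0568, p 0.8116 |
| Fisher, two-sided / one-sided | 1.000 / .603 | 1.000 / 0.6031 |

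The printed test is computed correctly.

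**3. Difference and interval under each reading.** Newcombe's interval uses the Wilson limits (l, u) of each proportion:

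lower = d - √[(p₁ - l₁)² + (u₂ - p₂)²]; upper = d + √[(u₁ - p₁)² + (p₂ - l₂)²]

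*Arms of 9 and 15.* p₁ = 2/9 = 0.2222 (Wilson 0.0632 to 0.5474); p₂ = 4/15 = 0.2667 (0.1090 to 0.5195); d = -0.0444.
- Lower: -0.0444 - √(0.1590² + 0.2528²) = -0.343
- Upper: -0.0444 + √(0.3252² + 0.1577²) = +0.317

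*Arms of 6 and 18.* p₁ = 2/6 = 0.3333 (0.0968 to 0.7000); p₂ = 7/18 = 0.3889 (0.2031 to 0.6138); d = -0.0556.
- Lower: -0.0556 - √(0.2366² + 0.2249²) = -0.382
- Upper: -0.0556 + √(0.3667² + 0.1858²) = +0.356

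**4. Sensitivity to the interval method** (95% limits in percentage points):

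| Method | 2/9 v 4/15 | 2/6 v 7/18 |
|---|---|---|
| Newcombe | -34.3 to +31.7 | -38.2 to +35.6 |
| Wald | -39.6 to +30.7 | -49.5 to +38.4 |
| Agresti-Caffo | -36.2 to +31.9 | -42.3 to +37.3 |
| Score (by mirroring the complementary table) | -39.1 to +35.0 | -44.9 to +36.6 |
| Exact unconditional, score test inverted on a 1-point grid | -37 to +34 | -42 to +38 |

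Every interval passes 30 points in both directions. The closest limit is 30.7 (Wald, arms of 9 and 15). Swapping arm or outcome labels only reverses the signs.

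**5. Odds ratio.** This is the same under both readings: (2 x 11)/(4 x 7) = 0.786. The conditional estimate is 0.79, with exact 95% interval 0.06 to 7.45. With labels swapped, the sample odds ratio is 1/0.786 = 1.27 and the interval becomes 0.13 to 17.5.

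**The case against.** The strongest reply is that the Summary is true as written. It reports the absence of a statistical difference and does not claim that the materials are equivalent, so the lack of an equivalence margin contradicts nothing. This stands. The fault is incomplete reporting, not a false statement; but it is the only conclusion offered, and it leaves the protocol's question unanswered.

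The 30-point figure comes from neither document, and one limit clears it only narrowly. That is also fair: it describes the intervals and is not a margin.

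The intervals treat the 24 cases as independent, while the protocol randomises subjects and the SAP counts teeth. Several teeth per child in the same arm would normally widen the intervals; teeth of one child in different arms could narrow them. This limits precision and does not remove the point.

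One labelling is more natural than the others. The planned 30:30 allocation favours arms of 9 and 15, and the 86.6% clinical success that the protocol cites for ferric sulfate suggests that success was the commoner outcome. That would give 7/9 v 11/15. Attrition could have unbalanced the arms, however, and which arm is MTA would still be unknown.

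The recall phrase concerns exfoliation grading, and the protocol uses the long-term label itself with visits to 12 months. Both are true, but the assessment time of these 24 cases is still not stated.

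Finally, the protocol's descriptive statistics could include rates by arm. None appears in the SAP, which nevertheless draws its conclusion.

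**Conclusion.** The concern holds, as something that should be fixed. The test is correctly computed and the sentence correctly reports non-significance, but a p-value alone cannot say which material succeeds more often or how far apart the two may be. The observed difference is 4.4 or 5.6 points in size, and its 95% interval extends beyond 30 points in each direction under both readings of the table and all five interval methods. The data are therefore compatible with a large advantage for either material, and a reader of the Summary would not know it. This rests on the table recovered from the printed output, which is unique up to labels, and on independence of the 24 cases. The missing recall time is a smaller, separate gap in the same sentence.

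**What to change.** Report clinical success as x/n in each arm, the risk difference and its 95% confidence interval (Newcombe or exact), and keep the test as a supplement. At the least, the counts, difference and interval must stand beside the p-value. Replace the Summary with wording such as:

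> Clinical success at [actual recall time of the 24 cases] was x/n with MTA and y/n with FS; difference d points (95% CI L to U). With 24 cases the study neither shows nor excludes a large difference between MTA and FS.

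Give the actual recall time, or its range, in place of the undefined long-term label.

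The cost is a change of SAP wording and a labelled 2x2 table. The software needed those counts to produce the output, so no new data are required. The price is a less definite headline.
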